1.2 Primary Study Endpoints

The primary endpoint is the number of sentinel nodes correctly identified with ICG and fluorescence imaging alone.

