1.3 Secondary Study Endpoints

Secondary endpoints include adverse events related to ICG and operative time for sentinel node biopsy.

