7.2.2 Operative Procedure

When the subject is in the operating room and appropriately sedated or anesthetized, he or she will receive a dermal injection of indocyanine green (ICG) 0.9 ml at the melanoma tumor site or subareola if breast cancer. Incision is made in the axilla or groin, and the SPY machine is positioned over the lymph node basin. Real-time lymphangiography (SPY) is used to identify sentinel nodes. Any fluorescent nodes should be resected and are considered sentinel nodes. The absolute fluorescence will be quantified for each sentinel node. Absolute fluorescence is calculated by the SPY machine.

After the sentinel lymphadenectomy is complete but prior to closing skin, the excised lymph nodes will be examined with the gamma probe (detects tech99 signal) to confirm that they are sentinel nodes. If the node does not have a signal with the gamma probe (but is fluorescent) it is still considered a sentinel node. The lymph node basin will also be examined with the gamma probe, to insure that no sentinel nodes are missed. If a gamma positive sentinel node is identified in the lymph node basin, it should be resected and imaged with SPY. If no sentinel nodes are able to be identified with fluorescent imaging, the gamma probe will be used as per usual practice. The surgeon should spend no more than 30 minutes using SPY to identify sentinel

nodes. If after 30 minutes no sentinel node is found, the gamma probe should be used. The data collection form (separately uploaded) should be completed for each case.

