8.3 Statistical methods

The analysis of these results will be descriptive. We will assess the number of nodes per patient that are correctly identified with ICG alone, and the number of patients in whom ICG was successfully used

alone. Multiple surgeons will be involved, some with more experience than others with this technique. We will assess the learning curve by studying the success rate with ICG over time for each surgeon.

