10.2 Data that are reviewed

Any adverse events that occur during surgery, whether deemed related to the ICG or not, will be reviewed. Adverse events will include reactions to ICG such as hives. Efficacy will be determined by success rates of localizing sentinel nodes with ICG alone.

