11.0 Risks

- Loss of confidentiality
- Adverse reactions to ICG are extremely rare, and none occurred in the prior trial with 87 subjects.
- Anaphylactic reactions, urticarial reactions and headache have been reported rarely in some patients.
- The risks of sentinel node biopsy are usual care as the subjects will undergo the biopsy regardless of their participation in the research. However, there is the possible risk of longer surgery, with a maximum of 30 additional minutes under anesthesia. This added time is of no consequence to the patient and carries an unmeasurable risk. Inaccurate identification of the sentinel node may occur equally in patients both on and off this study, therefore the risk in this study is no greater than usual care. The false negative rate in identifying sentinel nodes is 8%. Tech99 is used as a backup in this study in the event that the sentinel node cannot be identified with ICG.

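### The primary count cannot show an ICG false positive, and no planned output reports fluorescent, gamma-negative nodes or total nodes removed

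*Combined protocol and SAP*

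**What the plan says.** The primary endpoint (1.2) reads: "The primary endpoint is the number of sentinel nodes correctly identified with ICG and fluorescence imaging alone". Section 8.3 repeats it at patient level, "We will assess the number of nodes per patient that are correctly identified with ICG alone", and adds the number of patients in whom ICG alone succeeded. Neither section defines 'correctly'.

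The only working definition of a sentinel node is in 7.2.2. First: "Any fluorescent nodes should be resected and are considered sentinel nodes". After the dissection, "the excised lymph nodes will be examined with the gamma probe (detects tech99 signal) to confirm that they are sentinel nodes". The next sentence settles what a negative result means: "If the node does not have a signal with the gamma probe (but is fluorescent) it is still considered a sentinel node". The basin is then checked with the gamma probe, and any gamma-positive node still there is also removed and imaged.

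The other outputs are narrow. Section 1.3: "Secondary endpoints include adverse events related to ICG and operative time for sentinel node biopsy". In the monitoring plan, 10.2 says: "Efficacy will be determined by success rates of localizing sentinel nodes with ICG alone".

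On risk, 11.0 states: "The risks of sentinel node biopsy are usual care as the subjects will undergo the biopsy regardless of their participation in the research". It goes on to mention longer surgery and inaccurate identification, but not additional nodes. Section 5.1.1.2 has subjects told that both tracers find one and the same node.

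**The concern.** The gamma check is described as confirmation, yet a negative result cannot change a fluorescent node's status. All fluorescent nodes are therefore sentinel nodes by definition, and a node that only ICG marks adds to the primary count exactly as a node that both tracers mark.

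The question in 1.1 is whether ICG can be used alone. To answer it, a reader needs to know how often the two tracers mark the same nodes, how often ICG marks a node that tech99 does not, and the reverse. A single ICG count merges the first two. If ICG did lead to more nodes being removed, the count would rise or stay level, and nothing in the stated outputs would reveal it. This is the opposite error from a node that ICG leaves behind, so the gamma check of the basin does not cover it.

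**Working it through.** **Plan's own figure.** The sample size is 40 (8.1: 20 at one centre plus 20 across the other two; 20 + 20 = 40). Section 8.2 calls it a sample of convenience, so there is no power calculation to reproduce.

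**Step 1: can the count register a false positive?** By 7.2.2, a fluorescent node is sentinel if gamma-positive and sentinel if gamma-negative. The share of fluorescent nodes classed as sentinel is therefore 100% whatever the probe shows. Unless 'correctly' has some further meaning, which 1.2 and 8.3 do not give, the answer is no.

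**Step 2: is the information reported elsewhere?** Sections 1.2, 1.3, 8.3 and 10.2 list the ICG node count, patient-level ICG success, ICG-related adverse events, operative time and localization success rates. None lists total nodes removed or fluorescent, gamma-negative nodes.

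**Step 3: what could the ICG mean hide?** Inputs:

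- prior-trial means from 2.1: ICG 1.87 and tech99 1.89 nodes per patient;
- N = 40 from 8.1;
- *d*, the share of fluorescent nodes that are gamma-negative. The documents give no figure, so 0 to 20% is **assumed**.

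Per patient:

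- fluorescent-only = 1.87 × *d*
- positive on both = 1.87 × (1 − *d*)
- gamma-only = 1.89 − 1.87 × (1 − *d*)
- total removed = 1.89 + 1.87 × *d*, taking all fluorescent and all gamma-positive nodes as removed under 7.2.2

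| *d* (assumed) | Fluorescent-only per patient (in 40) | Both per patient (in 40) | Gamma-only per patient (in 40) | Total removed per patient | Reported ICG mean |
|---|---|---|---|---|---|
| 0 | 0 (0) | 1.87 (74.8) | 0.02 (0.8) | 1.89 | 1.87 |
| 5% | 0.09 (3.7) | 1.78 (71.1) | 0.11 (4.5) | 1.98 | 1.87 |
| 10% | 0.19 (7.5) | 1.68 (67.3) | 0.21 (8.3) | 2.08 | 1.87 |
| 20% | 0.37 (15.0) | 1.50 (59.8) | 0.39 (15.8) | 2.26 | 1.87 |

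Totals in 40 are computed before rounding: 40 × 1.87 × *d* = 3.74, 7.48 and 14.96, or about 4, 7 and 15 nodes. The last column is the same in every row: the planned node count would look identical under full agreement and under 20% discordance.

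**Step 4: do the prior means show an excess?** 40 × 1.87 = 74.8 and 40 × 1.89 = 75.6, a net difference of −0.8 nodes. They show no net excess from ICG. Near-equal means are, however, compatible with every row of the table, so they say nothing about concordance.

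**The case against.** A reader might infer something stronger: that ICG causes over-removal, that the trial scores it as success, and that the usual-care statement in 11.0 is therefore wrong. The documents do not support this.

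- The only data given show no net excess (1.87 against 1.89).
- Tech99 is not an error-free reference. Section 2.0 gives about 96% success for tech99 and blue dye together, and 11.0 cites an 8% false negative rate. A fluorescent, gamma-negative node may be a sentinel node that tech99 missed.
- Usual care is not tech99 alone. Section 2.0 describes tech99 with blue dye, and 15.1 says non-study patients may be charged for blue dye or ICG. Nodes marked by dye only can arise off study too, so the excess over usual care is unknown.
- Adding the two means gives a ceiling of 1.87 + 1.89 = 3.76 nodes per patient, but that requires the tracers never to mark the same node. It is a mathematical limit, not an expectation.
- Striking gamma-negative nodes from success would redefine the primary endpoint, which is debatable.

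Two further limits are fair. The patient-level result in 8.3 does not rise node by node. The data collection form is a separate document not available here, and it may already record gamma status per node, so the gap is shown only for the stated endpoints and analyses.

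All of this stands against the causal claim. None of it answers the reporting gap: not knowing what these nodes are is a reason to show them separately.

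**Conclusion.** The point holds as one of definition and reporting. The primary count as written cannot show an ICG false positive, and no stated output would reveal fluorescent-only nodes or total nodes removed. This rests on reading 'correctly' through the sentinel-node rule in 7.2.2, the only one the protocol offers.

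The size is unknown. About 4, 7 or 15 fluorescent-only nodes in 40 subjects is an illustration: it assumes discordance of 5, 10 or 20% and carries the prior means over, although in that trial all tracers were used simultaneously (2.0). Whether such nodes are a cost or a gain cannot be judged from the documents. The gap is worth closing because it is cheap to close, and agreement between tracers bears directly on the study question.

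**What to change.** 1. In 8.3, state how a fluorescent, gamma-negative node counts towards 'correctly identified'.
2. Beside the primary count, add a per-patient table: nodes positive on both tracers, fluorescent-only nodes, gamma-only nodes, total nodes removed, and the share of subjects with at least one fluorescent-only node. Say where a node belongs if it was found by the gamma probe in the basin and then fluoresced on imaging, since 7.2.2 provides for that case.
3. Optionally, show absolute fluorescence by gamma status. It is already quantified for each sentinel node, but with so few fluorescent-only nodes the comparison can only be descriptive.
4. Reconcile 11.0 and 5.1.1.2 with 7.2.2, which provides for nodes positive on one tracer only.

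The cost is one table and some wording. Every excised node is already examined with the gamma probe, but the result must be captured per node on the data form, which should be checked. The concordant count may look less favourable than the total ICG count. The sample size and the operative procedure, including the resection rule, are unchanged.

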2.0 Background

1.1 Scientific Background and Gaps

Sentinel node biopsy is a routine procedure in patients with both melanoma and breast cancer. The status of the sentinel node provides prognostic information and guides further treatment options in these patients. Sentinel node biopsy (SLN) was first developed using only a blue dye. Technetium99, a radioactive protein, was added later and provides the ability to image the patient and identify relevant lymph node basins. This feature is particularly important for trunk melanomas that can drain to multiple nodal basins. For the last 15 years or so, the standard method of SLN localization includes both tech99 and blue dye. While the rates of localization overall are excellent, these methods each have drawbacks.

Technetium 99 (tech99) is a radioactive protein that is injected dermally around the melanoma or the areola of the breast, usually one day prior to surgery. Lymphoscintigraphy is done 1-2 hours after injection and identifies the nodal basin that contains the sentinel node. Tech99 has an excellent track record of identifying sentinel nodes, but it does involve an extra trip to the hospital (patients are injected the day prior to surgery), the injection is often the most painful part of the entire treatment experience, and the signal can be vague and difficult to localize in the operating room. Furthermore, there are international concerns about the reliability of the supply of radio-labelled colloid. The reactors that currently provide tech99 and other radioactive substances are aging, and shortages of material have been threatened in the past.

Blue dye is injected dermally on the day of surgery, after the patient is anesthetized. This is a visual adjunct to the radioactive signal from the tech99. These two methods together have a success rate of approximately 96% in identifying the sentinel node. Blue dye alone localizes about 50% of sentinel nodes, and it can be problematic for the surgeon in that it stains tissues and is toxic to skin grafts.

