7.2 Study Procedures

7.2.1 Pre-op Procedure

Subjects will have a dermal injection of technetium99 (tech99) at the melanoma tumor site prior to surgery (either the day before, or morning of surgery) or a subareolar injection if breast cancer. The surgeon will not look at the lymphoscintigraphy films, and the radiologist should not mark the skin.

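### Section 8.3 counts ICG-alone success per patient without comparing the lymphoscintigraphy with the basin explored, so drainage to an unopened basin could pass as success

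*Combined protocol and SAP*

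**What the plan says.** The background (section 2.0, Scientific Background and Gaps) gives the scan its role: "Lymphoscintigraphy is done 1-2 hours after injection and identifies the nodal basin that contains the sentinel node". Section 7.2.1 then withholds it: "The surgeon will not look at the lymphoscintigraphy films, and the radiologist should not mark the skin".

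Section 7.2.2 describes the operation: "Incision is made in the axilla or groin, and the SPY machine is positioned over the lymph node basin". Fluorescent nodes are removed. Before the skin is closed, the probe is applied to the excised nodes and to the opened field: "The lymph node basin will also be examined with the gamma probe, to insure that no sentinel nodes are missed". Ordinary use of the probe has a separate trigger: "If no sentinel nodes are able to be identified with fluorescent imaging, the gamma probe will be used as per usual practice". The same applies if no node is found within the 30-minute limit. On recording, the section says: "The data collection form (separately uploaded) should be completed for each case".

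Section 8.3 plans a descriptive analysis with two counts: nodes per patient correctly identified with ICG alone, and "the number of patients in whom ICG was successfully used" alone. Section 10.2 adds: "Efficacy will be determined by success rates of localizing sentinel nodes with ICG alone". Neither section defines success for a patient.

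Section 2.1 gives the reason for opening one expected basin: drainage is treated as predictable for limb melanoma and breast cancer, but not for the trunk. Sections 3.1 and 3.2 restrict eligibility to match.

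**The concern.** The probe check can reveal a sentinel node that ICG missed in the basin that was opened. It is not directed at a basin that was not opened. The scan could show such a basin, but it is masked during surgery and no later step brings it back.

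The two possible outcomes are treated unequally. If the opened basin yields no fluorescent node, the failure is visible and the probe is used. If it yields one and the tumour also drains elsewhere, the available plan has nothing to show it. Any effect on the patient-level count is therefore upward.

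This bears on how the result will be used. Section 12.2 hopes to define patients who can do without tech99. Giving up tech99 means giving up the scan as well as the probe, so that hope rests on section 2.1's premise that the basin can be predicted. The scans that could test the premise in these 40 subjects are already obtained, but no planned analysis uses them.

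**Working it through.** **Step 1: where could a second basin come to light?** I looked at each place in the text where it might.

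- Section 7.2.2, after ICG success: the probe covers the excised nodes and the opened basin. Imaging of other basins is not requested.
- Section 7.2.2, after ICG failure: the probe is used as in usual practice. This branch is not reached once a node has been found.
- Section 10.1: the review after 10 subjects checks that sentinel nodes are being found. Films and basins are not mentioned.
- Section 10.6 (monthly review), section 18.5 (review of each data form) and section 20.1.1 (independent monitoring): none mentions films or basins.
- Section 8.3: no comparison of scan with basin explored.

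**Step 2: which quantities are affected?** The primary endpoint (section 1.2) is a count of nodes correctly identified. A node in an unopened basin is neither found nor counted, so the count does not rise. The secondary endpoints (section 1.3), ICG-related adverse events and operative time, do not depend on basin agreement. That leaves the patient-level count in 8.3.

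**Step 3: size, as an illustration only.** The one input from the documents is n = 40 (section 8.1), a sample of convenience (section 8.2). The share p of eligible subjects who also drain to an unopened basin is assumed. Expected number = 40p; chance that nobody is affected = (1 − p)^40.

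| Assumed p | Expected, 40p | None affected, (1 − p)^40 |
|---|---|---|
| 1% | 0.4 | 66.9% |
| 2% | 0.8 | 44.6% |
| 5% | 2.0 | 12.9% |

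**Step 4: effect on the reported rate.** Suppose ICG found every node in every opened basin, so that 40/40 would be reported. Each subject then counted as not a success moves the rate by 1/40 = 2.5 points. Exact (Clopper-Pearson) 95% limits are the 0.025 quantile of Beta(x, n − x + 1) and the 0.975 quantile of Beta(x + 1, n − x):

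- 40/40 = 100%: 91.2% to 100%
- 39/40 = 97.5%: 86.8% to 99.9%
- 38/40 = 95.0%: 83.1% to 99.4%

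If such subjects were removed instead, the results would be 39/39 and 38/38. Both are still 100%, with lower limits 0.025^(1/39) = 91.0% and 0.025^(1/38) = 90.7%. The coding rule and the denominator therefore have to be written down.

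**Step 5: what the comparison would yield.** If 0 of 40 subjects were discordant, the exact two-sided 95% upper limit would be 1 − 0.025^(1/40) = 8.8%.

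**The case against.** The strongest reply is that the plan faced unpredictable drainage and dealt with it through eligibility. Section 2.1 names the problem, and sections 3.1 and 3.2 exclude trunk, head and neck melanoma. The study is a descriptive pilot with no test and no success threshold, and patient-level success is not a listed endpoint. Success is also undefined: if it means that ICG found every sentinel node in the explored basin, a subject with a second basin is correctly a success. Finally, the data form is uploaded separately and may already record the scan.

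Much of this stands. Eligibility lowers the frequency, and the missing definition is a large part of the problem. But eligibility assumes predictable drainage without checking it, and section 3.1 includes sites up to the shoulder and groin. If the form does hold the fields, 8.3 still plans no comparison. In a purely descriptive study, the definition is what gives the count its meaning.

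Three stronger readings do not hold:

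- A reader might infer that the primary endpoint is biased. It is a node count and is not inflated.
- A reader might infer that the films are never recorded anywhere. The data form, the research data plan and the monitoring plan are not in the available text, so this cannot be said.
- A reader might use section 2.1's 47% visibility through the skin to calculate how many second basins would stay hidden. The text does not say whether that figure is per patient, basin or node, and nothing shows that it applies to a second basin.

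**Conclusion.** The gap holds in limited form. In the available text, nothing compares the withheld scan with the basin explored once ICG has found a node, so 8.3 could count a subject with drainage to an unopened basin as an ICG-alone success. That such a subject would be counted this way is an inference, because success is undefined.

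The effect is confined to the patient-level count and can only be upward. It is 2.5 points per affected subject, provided such subjects are coded as not a success over a fixed denominator of 40. How many there would be is unknown; the 1% to 5% range is an assumption, and at 1% it is more likely than not that nobody is affected. The larger loss is that the predictable-drainage premise goes untested although the scans exist. This is a minor point and a cheap improvement; it is no threat to the study's validity.

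**What to change.** Keep the surgeon masked during the ICG phase. After surgery, record two items if the data form does not already hold them: the basin or basins with uptake, from the existing scan or its radiology report, and the basin or basins explored.

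In section 8.3:

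1. Define patient-level success: at least one sentinel node found, and every sentinel node in the explored basin, whether fluorescent or gamma-positive, found by ICG without the probe.
2. Tabulate agreement between scintigraphic and explored basins.
3. Report success out of all enrolled subjects twice, with exact 95% intervals: once under that definition, and once with any subject who has an unexplored scintigraphic basin counted as not a success.
4. Report discordance as a result about basin prediction, separate from node-level ICG misses.

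The cost is a few data fields and a short table, with no new scan or procedure. Someone other than the masked surgeon should take the basins from the scan or report. Section 7.4.4 places all data collection in the operating room and would need a matching edit. The second success rate may be slightly lower, and 40 subjects can bound discordance only loosely (8.8% at best). The investigators must state how discordant findings are handled; no clinical rule is proposed here.

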7.3 Duration of Participation

Two days (pre-operative and operative procedure visits are associated with the research).

7.4 Test Article(s) (Study Drug(s) and/or Study Device(s))

7.4.1 Description

The SPY Elite machine is FDA approved for perfusion imaging. The PI has received permission from the FDA under IND number 114602 to perform this research study using a dermal injection of ICG. The ICG comes as a powder containing 25mg of indocyanine green and sterile water to reconstitute the powder for injection. Subjects will receive 2.25 mg of indocyanine green (ICG) in a volume of 0.9 mL.

7.4.2 Treatment Regimen

The patient will receive a dermal injection of indocyanine green (ICG) 0.9 mL at the melanoma tumor site or subareola if breast cancer while they are in the operating room under general anesthesia. This is a one-time injection so no dose adjustments will be made.

